4.5.3 Deaths, Other Serious Adverse Events, and Other Significant Adverse Events

All deaths during the study, including the post treatment follow-up period, will be listed by patient, to include the primary cause of death. Serious AEs and other significant AEs, including those that led to withdrawal, interruption, or dose reduction of either study drug, will be provided in separate patient data listings.

4.5.4 Clinical Laboratory Evaluation

All descriptive summaries of laboratory results will be based on data analyzed by the central or local laboratory and presented in Système International (SI) units, as suggested by the Center for Biologics Evaluation and Research and the Center for Drug Evaluation and Research *Position on Use of SI Units for Lab Tests* (Oct 2013). All data will be included in by-patient data listings. Laboratory measurements identified as abnormal (i.e., outside the normal range and ≥ Grade 3) will also be listed separately by patient, laboratory test, and unit. In addition, normal ranges provided by the central and local laboratories will be presented in a separate listing.

Clinical laboratory measurements, including serum chemistry, hematology, and coagulation will be summarized by study phase and cohort. Descriptive statistics will be presented for observed values and changes from baseline at each visit where parameters were scheduled to be collected per the clinical study protocol.

The cumulative number and percentage of patients with liver function test abnormalities meeting drug-induced liver injury (DILI) criteria will be summarized by treatment group. Patients meeting DILI criteria will also be presented in a patient data listing.

In addition, creatinine clearance will be calculated by the Cockcroft-Gault formula. For males, the creatinine clearance in mL/min will be calculated as $[(140 - \text{age}) \times \text{weight} (\text{kg})]/[72 \times \text{serum creatinine} (\text{mg/dL})]$. For females, the creatinine clearance in mL/min will be calculated as $0.85 \times$ the male value. The mean change from baseline over time for creatinine and creatinine clearance will be presented graphically over time by cohort and over all patients combined.

Where applicable, hematology and chemistry results will be classified as “low,” “normal,” or “high” with respect to the parameter-specific reference ranges (i.e., below the lower limit of the normal range, within the normal range, or above the upper limit of the normal range). Three-by-three contingency tables will be presented for each parameter to summarize the shift from the baseline category to the worst post-baseline measurement, defined as the value numerically farthest outside of the normal range across all post-baseline visits through the end of the study. Summary results will include the count and percentage of patients within each shift category and cohort.

Where applicable, hematology and chemistry results for select parameters will be assigned a toxicity grade based on the U.S. Department of Health and Human Services *Common Terminology Criteria for Adverse Events (CTCAE)*, version 5.0 (27 Nov 2017). If the quantitative criteria for grading are equivalent for two grades and the differentiation is described by clinical interventions, the clinical intervention component will not be considered and the highest CTCAE grade will be assigned. Similarly, death related to AE (i.e., Grade 5) cannot be determined with available laboratory-based data collection and, thus, will not be summarized as a category. Laboratory parameters that include multiple sets of criteria for each direction (e.g., separate criteria for potassium measures to assess hyperkalemia and hypokalemia) will be summarized separately to reflect each set of criteria.

Five-by-five contingency tables will be presented for lab tests where toxicity grading can be applied, to summarize the shift from the baseline grade to the worst post-baseline grade. Grades will be presented as none (Grade 0; i.e., measurements did not meet any CTCAE criteria for Grades 1 through 4), mild (Grade 1), moderate (Grade 2), severe (Grade 3), or life-threatening (Grade 4). Summary results will include the count and percentage of patients within each shift category.

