1.9. Valganciclovir

Valganciclovir (VALCYTE[®]), an oral prodrug of ganciclovir, is approved for treatment of CMV retinitis in patients with AIDS and prevention of CMV disease in high-risk transplant patients. Outside of its approved indications, valganciclovir has been shown to be effective in mitigating EBV viral load in EBV⁺ pediatric liver transplant patients at risk for development of post-transplant proliferative disorder.²⁰ Recommended adult dosing for treatment of CMV retinitis is 900 mg orally twice daily (BID) for 21 days followed by a maintenance dose of 900 mg once a day.

Oral valganciclovir is well absorbed (~60%) and converted to ganciclovir by first-pass intestinal or hepatic metabolism with peak plasma concentrations achieved in 1 to 3 hours. The major elimination pathway is renal excretion of ganciclovir through glomerular filtration and active tubular secretion. Dosage reductions, based on creatinine clearance, are recommended for patients with renal impairment. The antiviral activity of valganciclovir is based on the generation of ganciclovir-triphosphate, which is a competitive substrate for the CMV DNA polymerase. Significant AEs include hematologic toxicity and acute renal failure. Hematologic toxicity may result in leukopenia, neutropenia, anemia, and thrombocytopenia. The VALCYTE[®] package insert includes guidance regarding pre-treatment hematologic assessment and complete blood count (CBC) monitoring. Elderly patients, patients receiving nephrotoxic drugs and inadequately hydrated patients are at higher risk for renal failure. Other common AEs include gastrointestinal manifestations, such as diarrhea, nausea, and vomiting.

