No formal statistical analysis will be performed to compare cohorts. This study is exploratory in nature; descriptive statistics will be tabulated by study phase and cohort and reviewed to evaluate all study endpoints.

4.1.2 *Summarization by Visit*

In general, data summarized by study visit will be based on the nominal, scheduled visit label as reported on the eCRF. Data collected for the last patient visit will be summarized separately and this summary will be labeled as “End of Treatment” in the analysis.

For laboratory data summaries, data summarized by study visit will be based on the nominal, scheduled visit label as reported on the eCRF when available. If the scheduled visit is not available, then all data collection, including unscheduled and early

termination visits, will be reassigned a study visit based on the actual days relative to baseline using the visit windows identified in [Table 3](#) below.

Table 3 Visit Windows for Analysis

Scheduled Visit	Target Study Day	Study Day Interval
Baseline	0	≤ 0
Cycle 1 Day 1	1	1
Cycle 1 Day 2*	2	2
Cycle 1 Day 8	8	3 – 11
Cycle 1 Day 15	15	12 – 18
Cycle 1 Day 22	22	19 – XX^{**}
Cycle 2 Day 1	$XX + 1$	$XX + 1$
Cycle 2 Day 8	$XX + 8$	$(XX + 2) – (XX + 11)$
<hr/>		
...		

*Note Cycle 1 is the only cycle with a schedule Day 2 visit

** Day 22 is the last scheduled visit within each cycle, and the end of the study interval (XX) is calculated as the day before the start of the subsequent cycle.

If more than one value is mapped to the same visit, the value collected closest to the target study day will be considered for summarization. If two values collected on different days are mapped to the same scheduled visit and are equidistant from the target study day, the earlier of the values will be considered. The visit displayed on subject data listings will be reflective of the scheduled visit label as reported on the eCRF. Study days relative to baseline will be displayed for each visit to indicate to which visit the assessment may have been reassigned, if any.

Otherwise, data collected at unscheduled visits will not be included in by-visit summaries but will be considered when endpoint derivations potentially include multiple visits (e.g., determination of baseline value, determination of worst post-baseline value, etc.). All data will be included in patient listings.

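### The low/normal/high laboratory shift table takes one worst value across both directions, so a patient with a low count and a larger later rebound is counted only as high

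*SAP*

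**What the plan says.** SAP 4.5.4 classifies hematology and chemistry results as low, normal or high, meaning "below the lower limit of the normal range, within the normal range, or above the upper limit of the normal range". It then states: "Three-by-three contingency tables will be presented for each parameter to summarize the shift from the baseline category to the worst post-baseline measurement". The worst measurement is "defined as the value numerically farthest outside of the normal range across all post-baseline visits", up to the end of the study. The counts are reported by shift category and cohort.

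Two other provisions bear on how the rule works. Laboratory summaries are "presented in Système International (SI) units", and no scaling to the width or limits of the range is mentioned. SAP 4.1.2 keeps unscheduled results out of by-visit summaries but uses them in derivations that span visits, including "determination of worst post-baseline value, etc". A rebound seen at an unscheduled visit therefore counts.

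Later in SAP 4.5.4, CTCAE grades for select parameters get their own five-by-five shift tables. Parameters with criteria in each direction (potassium is the example) "will be summarized separately to reflect each set of criteria".

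**The concern.** The three-by-three table has two abnormal categories but allows each patient only one worst value. A patient who goes out of range in both directions has to be placed in one of them, and the rule chooses by raw distance. For quantities that cannot be negative, that choice favors the high side.

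The direction that can be lost is a relevant one. Of valganciclovir, Protocol 1.9 says: "Hematologic toxicity may result in leukopenia, neutropenia, anemia, and thrombocytopenia". Protocol 1.12.1 names thrombocytopenia as a toxicity that the two study drugs share. The trial can also produce a low value followed by recovery: both drugs are held for low counts (Protocol 5.1.8), myelosuppression may be treated at the investigator's discretion (Protocol 3.13), and the window for the worst value runs to the end of the study. Phase 1b cohorts hold at most 7 patients (Protocol 3.1.1), so one patient in the wrong column is at least 1/7, about 14%, of a cohort's row total.

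**Working it through.** The plan states no figure on this point, so there is nothing to reproduce. The check applies the rule as written.

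**Rule.** For a post-baseline value x, the distance outside the range is d(x) = max(LLN − x, x − ULN, 0). The worst value is the x with the largest d, and its side of the range gives the category.

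**When high replaces low.** With nadir N below LLN and a later value H above ULN, the patient is counted as high when H − ULN > LLN − N, that is, when H > ULN + (LLN − N). Since N cannot be below zero, LLN − N cannot exceed LLN. Any H above ULN + LLN therefore overrides every low value, including zero. This holds for any reference range.

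**Inputs.** The nadirs are set just under the hold thresholds in Protocol 5.1.8 (ANC 500/µL, platelets 35,000/µL, hemoglobin 8 g/dL), which in SI units gives 0.49 × 10⁹/L, 34 × 10⁹/L and 79 g/L. They serve only as reference points. The reference ranges are assumptions, because the documents leave them to the central and local laboratories.

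| Parameter | Assumed LLN | Assumed ULN | Nadir | High is chosen above (smallest to largest) | Any nadir overridden above (LLN + ULN) |
|---|---|---|---|---|---|
| Neutrophils, 10⁹/L | 1.5–2.0 | 7.0–8.0 | 0.49 | 7.0 + 1.5 − 0.49 = 8.01 to 8.0 + 2.0 − 0.49 = 9.51 | 8.5–10.0 |
| Platelets, 10⁹/L | 130–150 | 350–450 | 34 | 350 + 130 − 34 = 446 to 450 + 150 − 34 = 566 | 480–600 |
| Hemoglobin, g/L | 120–135 | 155–175 | 79 | 155 + 120 − 79 = 196 to 175 + 135 − 79 = 231 | 275–310 |

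**Worked patients (assumed ranges).**
- Neutrophils 0.3 then 10, range 1.5–7.5: 1.2 below against 2.5 above, shown as high. With a rebound to 8.5 it is 1.2 against 1.0, shown as low.
- Platelets 20 then 550, range 150–400: 130 below against 150 above, shown as high. With a rebound to 500 it is 130 against 100, shown as low.
- Potassium 2.4 and 6.2, range 3.5–5.0: 1.1 below against 1.2 above, shown as high. The low value leaves no trace in the table.

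**After the change.** With separate lowest and highest values, the patient with neutrophils 0.3 then 10 counts as low in the lowest-value shift and as high in the highest-value shift.

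**The case against.** The strongest answer is that the table is a coarse, generic display and severe low counts are reported elsewhere. A low/normal/high table carries no severity: with a lower limit of 1.8, neutrophils of 1.7 and of 0 both read as low. Severity belongs to the CTCAE shift tables, which do separate directions. SAP 4.5.4 also lists every abnormal value of Grade 3 or higher by patient, along with all laboratory data. On treatment, counts below the Protocol 5.1.8 thresholds lead to a hold, and Protocol 9.1.2 makes a laboratory abnormality that needs a hold an adverse event. It then enters the SAP 4.5.2 tables by grade and by dose interruption. Dose decisions rest on dose-limiting toxicities and Safety Review Committee review, and the analysis is descriptive throughout.

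Most of this stands, and it sets the limit of the point. A reader might infer that the plan conceals myelosuppression. The documents do not support that, given these other outputs. Nor do they support saying that the full set of low counts is expected from both study drugs: Protocol 1.12.1 names only thrombocytopenia and renal dysfunction as overlapping, and assigns anemia, leukopenia and neutropenia to one or both agents. Nothing in the documents says how often a rebound above the upper limit would occur.

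The objection does not make the count in this table right. CTCAE grading is planned for select parameters that the SAP does not name, and a listing does not correct a summary count. The SAP also already accepts, for the graded tables in the same section, that the two directions need separate treatment.

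**Conclusion.** The point holds as a small correction to one table. As written, the rule can move a patient with a low value into the high column and drop the low shift. The asymmetry follows from arithmetic and needs no assumed range; the numerical thresholds do. It also rests on reading numerically farthest as raw distance in reported units, which is the natural reading when no scaling is given.

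The error needs a rebound above the upper limit that is larger in absolute terms than the drop below the lower limit. That is plausible for neutrophils and white cells, possible for platelets and unrealistic for hemoglobin. Its frequency cannot be estimated from the documents. It does not reach the CTCAE tables, the listings, the adverse event summaries or any dose decision.

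**What to change.** In SAP 4.5.4, for parameters that can be abnormal in both directions (at least white cells, neutrophils, platelets and electrolytes), define the lowest and the highest post-baseline value separately and present a shift from baseline to each. A patient with both then appears in both. Alternatively, keep one table and add a post-baseline category for patients who were both low and high. Either option matches the separation by direction already planned for the CTCAE tables. Parameters where only one direction matters can keep a single shift, with that direction stated.

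The cost is a sentence or two in the SAP, minor programming and some additional table output. No new data are needed. The change should be made before database lock.

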3.7. Laboratory Procedures

Sites may elect to use either central or local laboratory tests for purposes of eligibility, safety, and other study required tests. The central laboratory kits should be utilized for the protocol-specified exploratory tests.

Any local labs collected for eligibility, or required by the study protocol, or to make treatment decisions will be entered into the electronic case report forms (eCRF).

The process for submitting central laboratory samples will be covered in the Laboratory Manual.

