7. SCHEDULE OF EVENTS

The study procedures for the Phase 1b and Phase 2 portions of the study will follow those outlined in [Table 15](#).

Table 15: Schedule of Events

Cycle	SR	1					2		3+		ET	ST	SV
Cycle Day		1	2	8	15	22	1	15	1	15			
Assessment													
Informed consent	X												
Medical history (includes donor data)	X												
EBER/histology sample	X						[X]		[X]		[X]		
Height	X												
Physical examination	X												
Symptom-directed exam		X	X	X	X	X	X	X	X	X	X	X	
Vital signs	X	X	X	X	X	X	X	X	X	X	X	X	
Performance status	X	X	X	X	X	X	X	X	X	X	X	X	
Adverse events		X	X	X	X	X	X	X	X	X	X	X	
Concomitant medications	X	X	X	X	X	X	X	X	X	X	X	X	
Urinalysis	X	X		X	X	X	X	X	X	X	X	X	
Hematology	X	X	X	X	X	X	X	X	X	X	X	X	
Chemistry	X	X	X	X	X	X	X	X	X	X	X	X	
Coagulation	X	X		X	X	X	X	X	X	X	X	X	
Serum pregnancy test	X												
Urine pregnancy test		X					X		X				
12-lead ECG	X	X	X	X	X	X	X	X	X	X	X	X	
Head CT/MRI	X												
Disease assessment	X								X		X		
PK sample(s)		X	X		X		X	X					
Urine PK sample collection		X											
Hepatitis B antigen/antibodies	X												
Hepatitis B DNA PCR	X												
Hepatitis C antibodies	X												
Hepatitis C qPCR	X												

Cycle	SR	1				2		3+		ET	ST	SV
HLA testing		X										
Exploratory Biomarkers												
-Histone H3 acetylation		X	X	X			X					
-Immune profile		X			X		X		X		X	
-EBV and CMV qPCR		X	X	X	X	X	X		X			
VRx-3996/valganciclovir distribution		X					X		X			
VRx-3996/valganciclovir return							X				X	
VRx-3996/valganciclovir compliance assessment		X	X	X	X	X	X	X	X	X		
Survival and follow-up assessment and disease status												X

Study assessments may be performed ± 3 days of the recommended date (however the DLT assessment period should include a full 28 days). Study visits with PK assessments should occur on days that the patient will take both study drugs, VRx-3996 and valganciclovir. End of Treatment (ET) Visit assessments (if needed) will be the same as for the Safety Follow-Up Visit. Safety Follow-Up Visit will be performed 28 ± 7 days after last dose.

SR – Screening (within 21 days of Cycle 1 Day 1)

ET – End of Treatment

ST – Safety follow-up

SV – Survival follow-up contact (performed at least every 3 months after safety follow-up assessment)

X – Required

[X] – Biopsy tissue samples taken per standard of care during study participation and samples taken at the time of relapse should be submitted to the central pathology lab for review.

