9. ASSESSMENT OF SAFETY

9.1. Specification of Safety Parameters

9.1.1. Adverse Event (AE) Definition

An AE is any untoward medical event that occurs to a patient following the start of investigational product (IP) administration, whether the event is considered IP-related or not.

Pre-existing conditions are not considered an AE unless the condition worsens by at least 1 grade following the start of IP administration.

Adverse events will be captured with the first dose of study drugs (on Cycle 1 Day 1) and continue until 28 days after the last dose of study drugs or until a new anticancer treatment is started.

Death considered related to disease progression will not be considered an AE. However, all deaths within 28 days of last study drug administration or assessed as related to study drug, must be reported on a serious adverse event (SAE) form within 24 hours.

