9.3. Time Period for AE Reporting

Adverse Events will be recorded that occur following the first administration of study drugs (on Cycle 1 Day 1) up to and including 28 days after the last dose of study drugs or until the start of a new anticancer therapy.

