3.4.1.1 Primary Safety Endpoints

An AE is any untoward medical event that occurs in a patient following the start of investigational product (IP) administration, whether the event is considered IP-related or not. Pre-existing conditions are not considered an AE unless the condition worsens by at least 1 grade following the start of IP administration. Adverse events will be captured with the first dose of study drugs (on Cycle 1 Day 1) and continue until 28 days after the last dose of study drugs or until a new anticancer treatment is started whichever is first.

Dose-limiting toxicity AEs must meet all of the following criteria:

- Occurs during the first cycle (28 days) of study drug administration in Phase 1b only
- Is not incontrovertibly related to underlying disease
- In addition, to be considered a DLT, the AE will meet at least one of the criteria listed below:
 - Grade 4 anemia unexplained by underlying disease
 - Grade 4 febrile neutropenia
 - Grade 4 neutropenia lasting >5 days
 - Any other Grade 4 hematologic toxicity (thrombocytopenia, neutropenia, febrile neutropenia, anemia) of any duration
 - Grade 4 or higher tumor lysis syndrome
 - Grade 3 or higher thrombocytopenia (with or without bleeding)
 - Any requirement for platelet transfusion
 - Grade 3 or higher non-hematologic toxicity despite adequate supportive care
 - Results in a dose hold of >7 consecutive days

AEs that persist <72 hours and are able to be managed with supportive care may be excluded.

3.4.1.2 *Secondary Safety Endpoints*

Laboratory Parameters

Clinical laboratory evaluations will follow those outlined in the clinical study protocol and will be performed using a central or local laboratory. Evaluations include hematology, chemistry, urinalysis, coagulation, and pregnancy tests (for women of childbearing-potential only). Specific parameters to be collected are listed below:

- Hematology (blood): Complete blood count with differential to include white blood cells and differential, red blood cells, hemoglobin, hematocrit, platelets, mean corpuscular hemoglobin, mean corpuscular volume
- Chemistry (blood): Sodium, potassium, chloride, bicarbonate, blood urea nitrogen, creatinine, glucose, calcium, phosphate, magnesium, aspartate aminotransferase (AST), aminotransferase, alanine aminotransferase (ALT), total bilirubin, alkaline phosphatase, total protein, albumin, uric acid, and lactate dehydrogenase

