4.5.5 Vital Signs, Physical Findings, and Other Observations Related to Safety

4.5.5.1 Vital Signs

Vital sign parameter measurements will be summarized by study phase and cohort. Descriptive statistics will be presented for results and change from baseline at each visit where parameters were scheduled to be collected.

4.5.5.2 12-Lead Electrocardiogram

Twelve-Lead ECG interval parameters will be summarized by study phase and cohort. Descriptive statistics will be presented for observed values and changes from baseline

at each visit where parameters were scheduled to be collected. For select visits, the ECGs will be performed in triplicate and the mean of these triplicate measurements at each timepoint will be used for summarization.

Twelve-lead ECG will be classified by the investigator as “normal,” “abnormal, not clinically significant,” or “abnormal, clinically significant.” Three-by-three contingency tables will be presented to summarize the shift from the baseline category to the worst post-baseline value. Summary results will include the count and percentage of patients within each shift category and cohort.

Prolonged QTc intervals will be summarized as QTc measurements (msec) that are >450, >480, and >500 at each visit where ECG is routinely collected per the clinical study protocol. Change from baseline categories will also be summarized for measurements that represent a change >30 or >60 relative to the baseline value. Summary results will include the percentage of patients within each category and cohort.

Clinically significant abnormalities occurring at any point in the study post-baseline will be presented in patient-data listings.

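### Worst-value laboratory and ECG summaries have no cut at new anticancer therapy, although AE collection does, so effects of the next regimen can enter the study-drug shift tables

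*SAP*

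**What the plan says.** **Adverse events.** Under SAP 3.4.1.1, AE capture starts at the first dose and will "continue until 28 days after the last dose of study drugs or until a new anticancer treatment is started whichever is first". Protocol 9.1.1 has the same limits ("continue until 28 days after the last dose of study drugs or until a new anticancer treatment is started"), as does Protocol 9.3 ("up to and including 28 days after the last dose of study drugs or until the start of a new anticancer therapy").

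**Laboratory category shift (3x3).** SAP 4.5.4 defines the worst post-baseline measurement as the one farthest outside the normal range, "across all post-baseline visits through the end of the study".

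**Laboratory grade shift (5x5) and DILI.** The same section sets the baseline CTCAE grade against the worst post-baseline grade, and counts cumulatively the patients who meet DILI criteria. Neither rule has an end date.

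**ECG shift.** SAP 4.5.5.2 will "summarize the shift from the baseline category to the worst post-baseline value", again without an end date.

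**What feeds these derivations.** SAP 4.1.2 keeps unscheduled visits out of the by-visit summaries but uses them to determine the worst post-baseline value. The notes to Protocol Table 15 state: "Safety Follow-Up Visit will be performed 28 ± 7 days after last dose". Hematology, chemistry and ECG are all marked at that visit.

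**The concern.** The same patient is assessed over two different safety windows. The AE window closes when another anticancer treatment begins. The laboratory and ECG worst-value window does not.

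Consider a patient who stops study drug for progression, begins cytotoxic treatment two weeks later, and has Grade 4 neutropenia at Safety Follow-Up. The neutropenia arose after AE collection closed, so it is not in the AE table. Nothing in the SAP keeps it from being that patient's worst neutrophil grade in the 5x5 table.

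Safety and tolerability is a primary objective. Protocol 1.12.1 names thrombocytopenia and renal dysfunction as toxicities shared by the two study drugs, and also lists anemia, leukopenia and neutropenia. Cytotoxic treatment can produce the same cytopenias, and with no control arm nothing in the data would reveal the mixture. The explanation may also be missing from the medication record, because Protocol 3.11 ends concomitant-medication recording at new anticancer therapy if that comes before 28 days.

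**Working it through.** No sample size, power or alpha figure in the plan depends on this point, so there is no stated figure to reproduce. The check compares the windows and then uses day arithmetic.

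**1. The windows side by side**

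| Output | End of window | Cut at new therapy? |
|---|---|---|
| AEs (SAP 3.4.1.1) | 28 days after last dose or new therapy, whichever is first | Yes |
| Laboratory 3x3 (SAP 4.5.4) | End of study | No |
| Laboratory 5x5 (SAP 4.5.4) | Not stated | No |
| DILI count (SAP 4.5.4) | Not stated | No |
| ECG 3x3 (SAP 4.5.5.2) | Not stated | No |

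The general statement in SAP 4.5 does not close the gap. For patients who do not complete the study, it includes all data available up to termination.

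**2. How next-regimen values can enter**

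- A Safety Follow-Up visit held after the next therapy has begun. Neither document requires the visit to come first.
- Unscheduled values, under SAP 4.1.2. Protocol 3.7 adds: "Any local labs collected for eligibility, or required by the study protocol, or to make treatment decisions will be entered into the" eCRF. This does not say that next-regimen tests are collected as such, but it excludes none made within its terms.
- Tests done to follow a laboratory AE. Protocol 9.1.2 continues these until the value is normal or explained, with no stop at new therapy.

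Survival follow-up is not a scheduled route. Protocol 6.3.3 allows it by records or contact, and Table 15 marks no laboratory test or ECG in that column.

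**3. Scheduled overlap with the next regimen**

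Let S be the day after last dose on which new therapy starts, and V the day of the Safety Follow-Up visit. V runs from 28 − 7 = 21 to 28 + 7 = 35. Overlap = max(0, V − S).

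| S | Overlap at V = 21 | Overlap at V = 35 |
|---|---|---|
| 1 | 20 days | 34 days |
| 7 | 14 days | 28 days |
| 14 | 7 days | 21 days |
| 21 | 0 | 14 days |
| 28 | 0 | 7 days |
| 35 or later | 0 | 0 |

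Unscheduled values have no upper limit in the text. Even without new therapy, a visit on days 29 to 35 lies up to 35 − 28 = 7 days beyond the AE window.

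**4. Effect per affected patient, at the planned group sizes**

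- Phase 2: 1/30 = 3.3 percentage points.
- Tablet cohort: 1/10 = 10 percentage points.

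**5. Number of patients affected**

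The documents give no rate of early next therapy and no rate of new abnormalities on it. As an assumption only, take the 25 + 30 + 10 = 65 planned patients. Suppose 10% to 50% start new therapy before their last laboratory test, and in 10% to 40% of those the worst category is set only by the next regimen. The result runs from 65 × 0.10 × 0.10 = 0.65 patients (1%) to 65 × 0.50 × 0.40 = 13 patients (20%). That range is too wide to serve as an estimate, and the conclusion does not use it.

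**The case against.** The strongest opposing case is that the exposure is narrow and the wide window is defensible. Routine tests stop at one Safety Follow-Up visit, so scheduled contamination requires new therapy to start before it. Eligibility requires that no available therapy offers a reasonable likelihood of significant benefit (Protocol 4.1), which makes quick subsequent chemotherapy less certain. The shift tables are descriptive and assign no cause. A long window is also conservative, because it retains delayed toxicity. All of this stands and limits the size of the problem. It does not supply the missing rule or justify closing one safety window at new therapy while leaving the others open.

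A reader might infer more than the text supports on these points:

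- **That the end-of-study wording also governs ECGs and CTCAE grades.** It appears only in the 3x3 laboratory rule. For the 5x5, DILI and ECG outputs the defect is an unstated end. The Grade 3/4 consequence belongs to the 5x5 table.
- **That the shift tables are the only objective count of these toxicities.** SAP 4.5.4 also gives by-visit laboratory summaries, a separate listing of abnormal values of Grade 3 or higher, and creatinine plots.
- **That any disagreement between laboratory and AE tables is an error.** Protocol 9.1.2 makes a laboratory abnormality an AE only under certain conditions, so the two will differ even with matched windows.

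**Conclusion.** The inconsistency is real and modest. The plan cuts AEs at new anticancer therapy, leaves the 3x3 laboratory shift open to the end of the study, and states no end for the 5x5, DILI and ECG derivations. Values caused by the next regimen can therefore be counted as the worst on study drug.

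The firm size is 3.3 percentage points per affected patient in Phase 2 and 10 in the tablet cohort, assuming the planned 30 and 10 patients are the denominators. The number affected cannot be computed. A reader might infer that such toxicity will be counted, or that Grade 3/4 rates will be inflated by some definite amount. The documents support neither: contamination requires early next therapy or late unscheduled tests, and no frequency is given for either. The short washout for entry in Protocol 4.2 (14 days, or 7 with approval) shows only that a quick change of therapy is possible, not how often patients leaving this trial make one.

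AE tables, DLTs (Phase 1b Cycle 1 only) and efficacy results are unaffected.

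**What to change.** In SAP 4.5.4 and 4.5.5.2, define one worst-value window for the laboratory 3x3, laboratory 5x5, DILI and ECG derivations:

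- It ends the day before new anticancer therapy starts, or at 28 days after the last dose if that is sooner or no new therapy is given.
- A scheduled Safety Follow-Up visit on days 29 to 35 is included as a stated exception to the AE cut-off, provided no new therapy has begun.
- The limit applies to unscheduled values as well.
- Later values stay in the patient listings, flagged as outside the window.

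For visits before new therapy, the exception leaves a deliberate difference of up to 7 days from the AE window. It should be stated so that day 29 to 35 results are not dropped by default.

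The cost is SAP wording and one date filter. The new-therapy date is already needed to censor PFS and DoR (SAP 4.6.5.2, Table 4). The downside is that a few late values that may reflect delayed study-drug toxicity leave the summary tables, though they remain visible in the listings. The change should be made before database lock.
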